### 9.2. Statistical analysis

For quantitative variables, descriptive statistics will be used (mean, standard deviation, minimum, median, maximum, 95% CI, and number of observations), whereas for categorical variables, frequencies and percentages analyses will be carried out. Results will be tabulated by treatment arm and pooled. The different vaginal formulations and progesterone will be formally compared. Results on efficacy and safety will be studied for each group separately and pooled, if relevant.

The proportion of women reporting adverse events during treatment will be cross-compared between the different doses using the Fisher's exact test or the Chi-square test.

All statistical analyses will be performed using the statistical software SPSS (Version 12) or Epistat 4.0.

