4. DOCUMENTS AND CHANGE OF VERSIONS

Version #	Date of Review	Date of Approval	Reason for Change
1.0	05Apr2017		N/A
2.0	21Apr2017		Additions to different sections
3.0	12May2017		English Version and clarification of some issues

CHANGES IN THE PLAN

At the moment there are no changes to the protocol or in the conduction of the study.

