11. SAFETY ANALYSIS

11.1 ADVERSE EVENTS

The evaluation of adverse events (AE) will be monitored throughout the study, by direct observation at each visit.

All AE will be recorded (according to the definition), and not only those where the investigator suspects a causal relationship with the treatment. Adverse events of interest; i.e., those in which the investigator at each site must pay particular attention are those that have been defined as local safety (pain, irritation, itching and infection) and major maternal complications attributable to the pessary as chorioamnionitis, severe vaginal or cervical trauma.

All the AE will be encoded in MedDRA version 19.1 or higher to be summarized by System Organ Class (SOC) / Preferred Term (PT).

The following 3 overview tables will be generated by treatment group and overall:

1) Summary of the number and percentage of subjects with at least 1:

- AE
- Serious AE
- Non-serious AE
- Unexpected AE
- Severe AE
- Related AE
- Related serious AE
- AE leading to discontinuation from IMP

The percentage denominator will be the number of subjects in the safety analysis.

2) Summary presenting the number of AEs per subject categorized as 0, 1, 2, 3, 4, 5, and >5;

3) Summary of the number and percentage of AEs for:

- AEs
- Serious AEs
- Non-serious AEs
- Unexpected AEs
- Related AEs
- Related serious AEs
- AEs leading to discontinuation from IMP

The percentage denominator will be the total number of AEs.

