11.2 INCIDENCE RATES AND NUMBER OF EVENTS

The incidence of an AE is defined as the number of subjects with occurrence of this AE during the period of interest. The incidence rate (CIR for crude incidence rate) of an AE is defined as the number of subjects with occurrence of this AE during the period of interest divided by the total number of subjects in the respective group (e.g., dose group).

The incidence, incidence rate, the number of events and the percentage of events (related to the total number of events) will be summarized by PT (sorted by decreasing incidence rate in the overall column) for

- AEs
- related AEs
- AEs leading to treatment discontinuation

A separate table per type of AE will be prepared. Only AEs occurring in at least 5% of subjects overall will be included in the text. Tables will be sorted by decreasing incidence overall.

The incidence, incidence rate, the number of events and the percentage of events (related to the total number of events) will be summarized by SOC and PT (sorted alphabetically) for each

- AEs
- serious AEs
- non-serious AEs
- related AEs
- serious treatment related AEs
- AEs leading to treatment discontinuation

For serious AEs, the incidence, incidence rate, the number of events, and the percentage of events will also be presented for serious treatment related AEs, serious fatal AEs and serious fatal related AEs.

For all enrolled subjects, the incidence, incidence rate, the number of events, and the percentage of events (related to the total number of events) will be summarized by SOC and PT (sorted alphabetically) for each.

The number and percentage of events will be summarized by SOC and PT (sorted alphabetically) for the following AE descriptors. Presentation will be for AEs only.

- intensity: mild, moderate, severe
- causal relationship to the imp: related (with subcategories: possible, probable/likely, certain), not related (with subcategories: not related, unlikely), unknown (with subcategories: conditional/unclassified, unassessable/unclassifiable, causal relationship missing)
- outcome: recovered/resolved, recovering/resolving, not recovered/not resolved, recovered/resolved with sequelae, fatal, unknown
- non-IMP related countermeasures: none, newly started medication, others
- action taken with imp: dose not changed, dose reduced, drug interrupted, trial discontinuation, unknown.

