Denominator for percentage calculation will be the number of all AEs for the presentation overall SOC, and the number of AEs per SOC or PT respectively, for the presentation per SOC or PT, respectively.

The following tables will be presented as part of this analysis:

- Table of AE that ended in discontinuation, presented by SOC and PT
- Table of AE presented PT
- Table of serious AE presented PT
- Table of non-serious AE presented PT
- Table of related AE presented PT
- Table of AE related and serious, presented PT
- Table of AE presented SOC and PT
- Table of serious AE presented SOC and PT
- Table of non-serious AE presented SOC and PT
- Table of related AE related, presented SOC and PT
- Table of related and serious AE presented PT
- Table of AE presented SOC and PT and intensity
- Table of AE presented SOC and PT and action taken
- Table of Unexpected AE (non-serious and serious) presented PT
- AEs by primary SOC, PT, and outcome
- AEs by primary SOC, PT and non-IMP related countermeasure
- AES by primary SOC, PT, and causal relationship to IMP

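### The protocol promises a test of the proportion of women with adverse events that SAP 11 does not plan, and SAP 11.2 shows intensity by event term only as a share of events

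*Protocol*

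**What the plan says.** **Protocol 9.2** commits to an inferential comparison: "The proportion of women reporting adverse events during treatment will be cross-compared between the different doses using the Fisher's exact test or the Chi-square test". Just before this it says: "The different vaginal formulations and progesterone will be formally compared".

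**SAP 11.1** describes the adverse event summaries: "The following 3 overview tables will be generated by treatment group and overall". Table 1 counts women with at least one event of each kind (any, serious, severe, related and others): "The percentage denominator will be the number of subjects in the safety analysis". Table 3 counts events, and there "The percentage denominator will be the total number of AEs".

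**SAP 11.2** defines a crude incidence rate as women with the event over women in the group. It tabulates this by PT for all events, related events and events leading to discontinuation, and by SOC and PT for those plus serious and non-serious events. Intensity, causality, outcome and action taken are handled differently. They are summarised by SOC and PT as numbers and percentages of events: "Denominator for percentage calculation will be the number of all AEs" at the overall level, and events within the SOC or PT below it.

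**SAP 4** says: "At the moment there are no changes to the protocol or in the conduction of the study". SAP 1 makes the protocol the final reference.

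**The concern.** Local and systemic safety in pessary users is a stated objective of both documents, and the capsule arm is the only comparator. A reader of the SAP tables will see the percentage of women with an event in each arm, but not the size of the difference or how uncertain it is. A programmer working from the SAP alone would not produce the comparison that the protocol commits to. If the test is added after the data are seen, the choice of test and of arms to compare is still open.

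The second issue is the denominator for intensity. A percentage of events says how an arm's events divide between mild, moderate and severe. It does not say how many women had a severe event. An arm with many mild events of a given term can therefore show the lower percent severe for that term even when more of its women had a severe one.

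**Working it through.** The documents give no adverse event rates, so there is no stated figure to reproduce. The check is textual, followed by illustrations with assumed counts.

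**1. Is the promised comparison planned anywhere in the SAP?**

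| Place | Content | Test, difference or interval for women with adverse events? |
|---|---|---|
| Protocol 9.2 | Fisher's exact or chi-square on the proportion of women | Yes, promised |
| SAP 5, general principles | Cochran-Mantel-Haenszel (CMH) for qualitative variables; follows the sentence on demographic and baseline comparisons | Adverse events not mentioned |
| SAP 10, secondary analysis | CMH for membrane rupture and for vaginal discharge | Only those two outcomes |
| SAP 11.1 and 11.2 | Counts, percentages, incidence rates | None |
| SAP 4 | No change declared | Promise not withdrawn |

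**2. Where does each per-woman figure appear?**

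| Kind of event | Women, overall | Women, by term |
|---|---|---|
| Any | Table 1 | By PT and by SOC/PT |
| Serious | Table 1 | By SOC/PT |
| Related | Table 1 | By PT and by SOC/PT |
| Severe | Table 1 | Nowhere; events only |

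So the per-woman gap by term is intensity.

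**3. Can the event percentage reverse the order?** Take one event term, 90 women per arm (the number per group in Protocol 9.1), and these assumed counts:

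- Arm 1: 40 events, 10 of them severe, in 10 women.
- Arm 2: 120 events, 20 of them severe, in 20 women.

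Percent of events that are severe: 10/40 = 25.0% against 20/120 = 16.7%, so arm 2 looks better.
Percent of women with a severe event: 10/90 = 11.1% against 20/90 = 22.2%, so arm 2 is worse.

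**4. Does the choice of test matter?** For 10/90 against 20/90, the uncorrected chi-square is

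180 × (10×70 − 20×80)² / (90 × 90 × 30 × 150) = 180 × 810,000 / 36,450,000 = 4.00, p = 0.046.

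Fisher's exact test on the same table gives p = 0.071. The two permitted tests fall on opposite sides of 0.05.

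**5. What would an interval add?** For the same table the difference is 11.1 percentage points. The Wald standard error is √(0.111×0.889/90 + 0.222×0.778/90) = 0.0549, so the 95% interval is 11.1 ± 1.96 × 5.49, or 0.3 to 21.9 points. At 90 women per arm the half-width is largest when both rates are 50%: 1.96 × √(2 × 0.25/90) = 14.6 points.

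**6. How much can the test detect?** Power at 90 per arm, two-sided 0.05, assumed rates:

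| Rates | Chi-square | Fisher |
|---|---|---|
| 10% v 20% | 0.47 | 0.40 |
| 10% v 25% | 0.76 | 0.71 |
| 20% v 40% | 0.84 | 0.80 |

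Three pairwise tests at 0.05 would have a family-wise error of 1 − 0.95³ = 14.3% if independent, so they should be labelled unadjusted.

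**The case against.** The strongest reply is that the SAP already reports safety per woman in most places. That is correct, and it limits the point in two ways.

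- A reader might infer that no table shows whether more women had adverse events with a pessary. Table 1 of SAP 11.1 shows exactly that, by arm, for any, serious, severe and related events. What it lacks is the difference and its uncertainty.
- A reader might also extend the denominator complaint to causality. SAP 11.2 gives related events per woman by PT and by SOC/PT. Only the finer causality grades are event-based, so causality is not part of this point.

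It can also be said that the intensity tables print event counts beside the percentages, so a careful reader could notice the imbalance. That reduces the risk of a misreading, but event counts still do not give the number of women.

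On the missing test, the general CMH sentence in SAP 5 could be read as covering every qualitative variable. Unstratified, CMH equals Pearson's chi-square times (N − 1)/N; in the example above, 4.00 × 179/180 = 3.98, so it is practically the promised chi-square. But the sentence sits with the baseline comparisons and does not mention adverse events. Where SAP 10 wants CMH for a particular outcome it says so, and SAP 11 does not. Because the protocol is the final reference, the commitment stands. It has been left out of the SAP, not withdrawn.

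On the wording about doses, Protocol 9.2 speaks of comparing the formulations formally, and Protocol 6 lists the capsule among them. Including the control is thus the likelier intention. The adverse event sentence still does not say so, and clarifying it costs nothing.

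Finally, p-values for every row and contrast would go beyond the protocol, which promises a test of one quantity. This objection stands, and the fix is limited accordingly.

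**Conclusion.** The point holds in a limited form. The SAP omits a between-arm comparison of women with adverse events that the protocol promises and that no change log withdraws. The protocol sentence leaves both the arms and the choice of test open. Intensity by event term has no per-woman version.

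The documents do not fix the size of the effect on interpretation. All rates and counts in the illustrations are assumed. They show that the order of two arms can reverse (25.0% v 16.7% of events; 11.1% v 22.2% of women) and that the open choice of test can decide nominal significance (0.071 v 0.046). They do not show that either will happen in this trial. At 90 women per arm, only large differences in adverse event rates would be detected reliably, so the confidence interval is more useful than the p-value.

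**What to change.** 1. **SAP 11.1, table 1.** On the any, serious, severe and related rows, add the risk difference with 95% confidence interval for B v A, C v A and C v B (SAP labels; A is the capsule arm). That is 4 rows × 3 contrasts = 12 intervals. State the interval method, since an interval and an exact test can disagree near 0.05, as they do in the example. Give the protocol's p-value on the any-event row only, for the three contrasts, with one named test (for example Fisher's exact), labelled unadjusted and descriptive.
2. **SAP 11.2.** Add intensity by SOC and PT as women at their worst intensity for that term, over women in the arm, and keep the event counts alongside. Protocol 8 already records the maximum intensity of each event, so no new data are needed.
3. **Protocol 9.2.** Replace the reference to doses with the three arms, and name the same test as the SAP.

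The cost is a few lines of SAP text, one clarified protocol sentence and some table programming. The downside is a small number of unadjusted safety comparisons, which the label must make plain.

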#### 5.6. Adherence and resuming the treatment in patients assigned to the group treated with vaginal progesterone capsules.

Use of capsules at least during 80% of the exposure time, and resuming the treatment not later than 72 hours after discontinuation for any cause will be considered an acceptable adherence to treatment. If adherence of a patient is below 80% or the treatment is interrupted for more than 72 hours, she will be withdrawn from the study but considered in the final statistical analysis.

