#### 5.7. Study participant withdrawal

The progesterone cerclage pessary will be removed if the patient requests so, or if there is any adverse event not responding to treatment alternatives such as pathological vaginal discharge non-responsive to antibiotic therapy. These participants will not be replaced and the information collected from them will be included in the analysis since this is based on the intention-to-treat principle.

Follow-up of subjects withdrawn from the investigational product will be the same as the standard follow-up.

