## 8 ADVERSE EVENTS

An adverse experience is defined as an unfavorable and unexpected change in the structure, function, or chemistry of the body, transiently associated with the use of the study product, whether or not related to the use of the drug. Any worsening (i.e., any adverse change clinically significant in terms of frequency or severity) of a pre-existing condition that is transiently associated with use of the study product is also an adverse experience.

Adverse events will be documented from the time of enrollment (i.e., at the time of signing the informed consent form) through the last scheduled contact as per the protocol, i.e., the date of the last visit/contact (may be a phone call, for example, in case the participant withdraws from the study).

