9. TREATMENT COMPLIANCE

For Group A, at the start of each visit, it will be recorded the number of capsules dispensed at the previous visit and the number of capsules used, the treatment compliance will be estimated in percentage. The compliance should be between 80 and 120% for each patient.

For groups B and C, it will only be recorded if removal of the pessary was necessary. In this case the subject will be early terminated from the study and the reason for discontinuation will be recorded.

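### Adverse events are analysed only as crude proportions of women, over a counting window that the two documents define inconsistently, so arms with unequal time at risk would not be comparable

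*Protocol*

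**What the plan says.** Protocol 9.2 makes the adverse event comparison one of proportions: "The proportion of women reporting adverse events during treatment will be cross-compared between the different doses", "using the Fisher's exact test or the Chi-square test". The same section says in general terms that the formulations will be formally compared and that safety will be examined by group and pooled.

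SAP 11.2 calls its measure an incidence rate, but it is a proportion: women with the event in the period of interest, "divided by the total number of subjects in the respective group". That period is not defined. SAP 11 specifies tables and no between-arm test.

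On how long women are observed for adverse events:
- Protocol 8 records events from consent "through the last scheduled contact as per the protocol".
- Protocol 5.7 gives women withdrawn from the product the standard follow-up.
- SAP 9 says of pessary removal: "In this case the subject will be early terminated from the study and the reason for discontinuation will be recorded".
- Protocol 5.4.5 closes every case at 36 6/7 weeks or at preterm birth, whichever arm the woman is in.

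On stopping, Protocol 5.7 begins: "The progesterone cerclage pessary will be removed if the patient requests so", and adds adverse events that do not respond to treatment. Protocol 5.5 adds expulsion not corrected within 72 hours and labour not responding to tocolytics. For capsules, Protocol 5.6 withdraws a woman under a different rule: "If adherence of a patient is below 80% or the treatment is interrupted for more than 72 hours".

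**The concern.** A crude proportion counts a woman observed for two weeks as one full unit of denominator, the same as a woman observed for twenty. Arms can be compared on that scale only if time at risk is similar, or if everyone is followed for the same period whether or not she is still treated. The plan secures neither and reports nothing that would let a reader check.

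There are two routes to unequal time at risk. Pessary and capsule women stop under different rules. Delivery also ends observation, and SAP 10 expects preterm birth to be least frequent on the higher-dose pessary and most frequent on capsules. The first route can make an arm with more early stopping look safer. The second can make a more effective arm look less safe.

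Local and systemic safety and tolerance of the device are secondary objectives, so these percentages will be read as results.

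**Working it through.** **The counting window, side by side**

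| Place | Are events after treatment stops counted? |
|---|---|
| Protocol 8 | Yes, to the last contact |
| Protocol 5.7 | Yes by implication: standard follow-up continues |
| Protocol 5.5, 5.6 | Unclear: withdrawn from the study but kept in the final analysis |
| Protocol 9.2 | No: treatment period only |
| SAP 9 | No for pessary women: participation ends at removal; no such statement for capsule women |
| SAP 11.2 | Undefined |

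The protocol alone gives two answers, and the SAP adds a third that differs between pessary and capsule.

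**Inputs**

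Planned pessary time runs from insertion (week 16 to 24) to 36 6/7 weeks, so 36.86 − 16 = 20.9 down to 36.86 − 24 = 12.9 weeks, the same for both doses. The documents give no adverse event rate, no early-stopping share by arm and no sample size reasoning for safety, so there is no planned figure to reproduce. The only anchor is Protocol 9.1: up to 10% may not complete, not split by arm. Everything below that is not from the documents is an assumption.

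**Route 1: early stopping, events after stopping not counted**

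Assume a constant event rate, 40% of women with an event over a full course, and early stops spread evenly over the course and unrelated to events. With cumulative hazard h = −ln(0.6) = 0.511 and share s stopping early:

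crude proportion = (1 − s)(1 − e^−h) + s[1 − (1 − e^−h)/h]

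Here 1 − e^−h = 0.400 and the second bracket is 1 − 0.400/0.511 = 0.217.

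| s | Calculation | Crude proportion |
|---|---|---|
| 0% | 0.400 | 40.0% |
| 5% | 0.95 × 0.400 + 0.05 × 0.217 | 39.1% |
| 10% | 0.90 × 0.400 + 0.10 × 0.217 | 38.2% |
| 20% | 0.80 × 0.400 + 0.20 × 0.217 | 36.3% |
| 40% | 0.60 × 0.400 + 0.40 × 0.217 | 32.7% |

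The true rate is identical in every row. At 10% v 5% the artefact is 39.1 − 38.2 = 0.9 points. At 20% and 40% it is 3.7 and 7.3 points against an arm with no early stops, or 2.8 and 6.4 against an arm with 5%.

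With a truly 1.5-fold higher rate, the full-course figure is 1 − 0.6^1.5 = 53.5%, and the same formula gives 48.8% at s = 20% and 44.2% at s = 40%. Part of a real excess is hidden.

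Varying the assumed event proportion P, with stopping in one arm only, at a quarter or half of the course (c = 0.25 or 0.5), the shortfall is s[P − (1 − (1 − P)^c)]:

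| P over full course | 10% stop early | 30% stop early |
|---|---|---|
| 20% | 0.9 to 1.5 points | 2.8 to 4.4 |
| 30% | 1.4 to 2.1 | 4.1 to 6.4 |
| 50% | 2.1 to 3.4 | 6.2 to 10.2 |
| 70% | 2.5 to 4.4 | 7.4 to 13.2 |

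**Route 2: prolonged pregnancy**

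Assume a start at week 20, births before week 34 in 40% v 20% of women, and those births at week 30 on average. Full exposure is 16.86 weeks; an early birth leaves 10. Mean exposure is 16.86 − 0.4 × 6.86 = 14.1 weeks v 16.86 − 0.2 × 6.86 = 15.5 weeks. With equal event rates and P = 30%, a woman delivering early has a risk of 1 − 0.7^(10/16.86) = 19.1%. The arms show 0.6 × 30 + 0.4 × 19.1 = 25.6% and 0.8 × 30 + 0.2 × 19.1 = 27.8%. The more effective arm looks 2.2 points worse; at P = 70% the figure is 3.8 points.

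**The case against.** The strongest defence is that the protocol keeps observing women after treatment stops (sections 8 and 5.7) and that SAP 1 makes the protocol the final reference. If events after stopping are counted, most of route 1 disappears. This stands as far as it goes, but Protocol 9.2 itself restricts the comparison to the treatment period, so deferring to the protocol does not settle the window. Route 2 remains in any case, because preterm birth closes the case.

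Several stronger readings are tempting and are not supported:
- *That time on treatment does differ by arm.* The documents show how it could, not that it will. The test named in Protocol 9.2 is between doses, and both pessary doses share the same insertion window and removal rules. Differing stopping rules apply only to pessary v capsule; the two doses could diverge through delivery.
- *That the plan is biased toward no harm exactly when the device is poorly tolerated.* A woman whose pessary comes out because of an adverse event is already counted for that event; only later or different events can be missed. Intolerance also shows elsewhere: events leading to discontinuation are tabulated (SAP 11), and expulsion and removal requests are separate outcomes (Protocol 7.2.3).
- *That the distortion is large.* At 10% v 5% stopping it is under a point. The larger figures need 20% to 40% stopping, which nothing in the documents predicts.
- *That an on-treatment rate should replace the crude comparison.* It would discard events after removal, and it misleads if events cluster at insertion. With equal true rates, half the cumulative hazard in the first tenth of the course, and 40% v 5% stopping, the rate ratio comes out at about 1.09, a false signal of harm.

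It is also fair that in an exploratory phase II study crude percentages are a reasonable description.

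**Conclusion.** The point holds in limited form. Both documents rest the adverse event analysis on crude proportions, neither takes account of time at risk, and the counting window is contradictory. The proportions can be compared only if time on treatment and follow-up turn out similar across arms, and the plan provides nothing to show whether they did.

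The direction of any bias is not fixed: uncounted time after stopping favours the arm that stops earlier, while longer pregnancy counts against the more effective arm. The stopping effect is under 1 point at 10% v 5%, and about 4 to 7 points if 20% to 40% stop early in one arm and none in the other. This rests on a 40% event proportion, a constant rate, evenly spread stops unrelated to events, and no counting after stopping. The delivery effect is 2 to 4 points under the birth rates assumed above. The contradiction in the window needs no assumption and is the firmest part of the finding.

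**What to change.** 1. Reconcile Protocol 8, 5.5, 5.6, 5.7 and 9.2 with SAP 9 and 11.2, and state one adverse event counting window, identical in all arms, that includes time after treatment stops. Define the period of interest in SAP 11.2 accordingly. This concerns what is counted; it does not change when any treatment is stopped.
2. Record the last treatment date for every woman, and report time on treatment and length of follow-up by arm.
3. Keep the crude percentages as planned.
4. For any adverse event, related events, serious events and the named local safety events, add cumulative incidence of the first event since start of treatment, by arm. As a supporting analysis, add first events per woman-week with a rate ratio and 95% CI. Show both on-treatment and over all follow-up.

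The cost is SAP wording, a few extra table columns and one model per event group. Much of the data is already collected: dates of removal requests and of unreplaced expulsions (Protocol 7.2.3), and capsule counts (SAP 9). The rate ratio assumes a constant rate; the cumulative incidence curves check that, and they should lead if events cluster around insertion.
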